Experimental procedures – PET/CT imaging studies will be performed on two separate days. These studies will be performed as close as possible to each other (e.g., within 1-2 weeks) and within the luteal phase for pre-menopausal women). Studies will be performed in the morning (~7 am). Participants will be asked to fast overnight (12 h) and refrain from strenuous physical activity for 48 h prior to the study day. A urine pregnancy test will be performed (premenopausal women) prior to initiating study procedures. Clothing will be standardized, with participants clad only in slippers socks, shorts, and a short sleeve t-shirt. During Visit #1, BAT activity under thermoneutral (room temperature) conditions will be determined by administering a single dose of ¹¹C-acetate and quantifying the decay using dynamic PET. A regional CT scan will also be performed to define the regions of interest. During Visit #2, BAT activity following cold-exposure will be determined by administering a single dose of ¹¹C-acetate and quantifying the decay using dynamic PET. BAT volume and activity will then be determined by administering a single dose of ¹⁸F-FDG followed by another dynamic PET scan, and then whole body static PET and whole body CT scan (eye level to knee caps)

Visit #1 (Thermoneutral conditions, Figure 6a) – Participants will report to the Colorado Research Imaging Center at 8:00 AM. Upon arrival, a urine pregnancy test will be performed in pre-menopausal

[figure not shown]

Figure 6a. Thermoneutral Condition

[figure not shown]
volunteers. A fasted blood sample will be obtained for the measurement respiration and protein measures of mitochondrial markers, then FMD and C-IMT will be performed.

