(40 mA.s) centered at the cervico-thoracic junction to correct for attenuation and to define PET ROI. At time 150 minute, a 2 minute PET frame will be performed to account for any residual ^{11}C -acetate. A ~ 185 MBq i.v. bolus of ^{18}FDG will then be administered followed by a 30 minute dynamic mode PET scan. At time 180 min, participants will be instructed to void to minimize radiation exposure (30 min. after ^{18}FDG administration). A whole body CT scan (16 mA.s) and whole body static PET acquisition will then be performed to determine whole body ^{18}FDG organ distribution and tissue SUV. To minimize radiation exposure, participants will be instructed to void a second time as soon as the study is completed (2 hrs. after ^{18}FDG administration).

Pre-menopausal women participating in the intervention study will repeat the PET/CT studies after 6 month of ovarian hormone suppression (Visits #9 and 10).

PET/CT image analysis - [name], a co-I in the Department of Radiology, will oversee data acquisition of all PET images and analysis of whole-body FDG PET acquisitions, with the guidance of our collaborator [name]. Drs. [name] and [name] will provide additional guidance in the analysis and interpretation of the ^{11}C -acetate data and the ^{18}FDG dynamic PET data.

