GnRH_{AG} therapy – Fifteen premenopausal women will be recruited from the cross-sectional study to participate in the longitudinal study. Following the next menses after baseline testing, participants will initiate 6 mo of GnRH_{AG} therapy (intramuscular injection of leuprolide acetate 3.75 mg for depot suspension; Lupron; TAP Pharmaceutical Products, Inc.; Lake Forest, IL) to chronically suppress ovarian hormones. A single injection of leuprolide acetate produces an initial stimulation (for up to 3 wk) followed by a prolonged suppression of pituitary gonadotropins and ovarian hormones. Repeated monthly dosing suppresses ovarian hormone secretion. GnRH_{AG} therapy has been used clinically for up to 1 year without serious adverse events, although there is a decrease in BMD that recovers following cessation of treatment.^{34,79} The drug is used for the management of endometriosis and for pre-operative management of anemia caused by uterine fibroids. Side effects are those typical of hypoestrogenemia. In studies of women with uterine fibroids, GnRH_{AG} 3.75 mg/mo. induced amenorrhea in 61%, 86%, and 90% of women after 1, 2, and 3 mo of treatment, respectively.^{28,74} Return of menses typically occurs within 1 to 3 mo of cessation of therapy.

Absence of pregnancy (urine test) will be confirmed before each dosing. Participants will be observed for 30 min after drug injection to monitor for hypersensitivity reactions. Women who do not tolerate GnRH_{AG} therapy in the proposed study can refuse further treatment after each monthly dosing. Among the first 94 women treated with GnRH_{AG} in our previous and ongoing studies (R01 AG018198, P50 HD073063), this

occurred only once. Participants will also meet with the study research nurse practitioner, providing a regular mechanism by which adverse events will be queried. A health status questionnaire will be used to track changes in use of medications (prescription and over-the-counter) or health (e.g., doctor visits, hospitalizations), as well as any study-related problems/concerns over the past 4 weeks. Participants will also complete a Menopausal Symptom List (MSL) to monitor the frequency and severity of menopause-related symptoms (e.g., hot flashes, depressed feelings); the Eating Behavior Questionnaire (EBQ) to monitor dietary restraint, disinhibition, and hunger;⁷⁸ and the Pittsburgh Sleep Quality Index (PSQI) to monitor sleeping behavior.¹²

Potential risks

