Core temperature pills: Participants will be advised to avoid having an MRI test for at least a week after the study. Because the capsule is a radiotransmitter, participants will also be advised to avoid travel on commercial airlines for at least a week after the study. The recording device is electrically isolated and complies with hospital standards for electrical safety.

sEMG and skin temperature sensors: Any skin irritation from the sensors is expected to be minor and temporary.

Confidentiality and privacy: These risks will be minimized by not including personal identifying information on the forms, when possible, and by conducting interviews and collection of personal information in a private setting.

Evaluation of study-related events – The subset of premenopausal women enrolled in the intervention study will meet with a study clinician every 4 weeks to review a Health Status Questionnaire that the participants will complete. The questionnaire queries about changes over the past 4 weeks in medications, health status, and any concerns with study medications. The clinician will specifically note on the form whether there are any concerns that are possibly, probably, or definitely related to the study. Participants will also be instructed to report concerns that may be study related when they occur to the research nurse practitioner, [name], who will initiate event reports for both the programmed and spontaneous complaints.

E. Potential Scientific Problems:

We considered studying women across the menstrual cycle, rather than a cross-sectional comparison of pre- vs. postmenopausal women. The strength of the cross-sectional design is that postmenopausal

women will have been estrogen deficient for several years, which should maximize the attenuation of E₂ deficiency on BAT activity. A limitation is that we will not be able to determine whether this is also partially due to age. However, if the exploratory aim confirms that GnRH_{AG} reduces BAT activity, this will support the overall hypothesis that E₂ deficiency, rather than age, is the primary factor contributing to reduced BAT in postmenopausal women.

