Analysis strategy - Statistical analyses will be performed using SAS 9.4. Analyses will begin with descriptive plots of individual variables to evaluate distributional characteristics and for quality assurance. The effect of menopausal status on each endpoint will be estimated using a linear regression model. The endpoint will be the response variable and a variable indicating menopausal status will be the explanatory variable (equivalent to a 2-sample t-test). If a variable that is related to the response variable is not balanced between menopausal groups, that variable will be included in the regression model to eliminate the potential of the effect of menopausal status being confounded by that variable. For all multivariable analyses, regression diagnostics will be used to ensure that the group of explanatory variables are not collinear. Secondary analyses will be performed to investigate whether REE is associated with either BAT

oxidative metabolism or BAT activity volume. Exploratory analyses will investigate the changes in BAT oxidative metabolism and BAT volume of activity associated with GnRH_{AG} treatment (Aim 3) Because these aims are exploratory, results will be reported using descriptive statistics, mean change, and 95% confidence intervals (CIs) for the changes in the primary and secondary endpoints.

G. Summarize Knowledge to be Gained:

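### A fall in BAT activity after GnRH agonist in the 15-woman SA3 could suggest that ovarian hormone loss contributes; it cannot show that E2 deficiency, rather than age, is the primary factor

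*Combined protocol and SAP*

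**What the plan says.** Section IV.E (Potential Scientific Problems) explains the choice of a cross-sectional comparison and admits its weakness: "A limitation is that we will not be able to determine whether this is also partially due to age". The next sentence offers SA3 as the remedy. If the exploratory aim confirms that the agonist reduces BAT activity, this is to support the overall hypothesis that E2 deficiency, "rather than age, is the primary factor contributing to reduced BAT in postmenopausal women".

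The SA3 design is in Section IV.D. "Fifteen premenopausal women will be recruited from the cross-sectional study to participate in the longitudinal study", and these women "will repeat the PET/CT studies after 6 month of ovarian hormone suppression". No untreated, placebo or E2 add-back group is described. On the drug, the section says: "Repeated monthly dosing suppresses ovarian hormone secretion". Imaging is scheduled "within the luteal phase for pre-menopausal women".

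The analysis is in Section IV.F (Analysis strategy). For Aim 3, "results will be reported using descriptive statistics, mean change, and 95% confidence intervals (CIs) for the changes" in the primary and secondary endpoints. No size of change is set for the word *confirms*, and no comparison with the SA1/SA2 difference is planned.

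**The concern.** The word *primary*, set against age, is a statement about relative size: that hormone loss accounts for more of the pre/post difference than age does. SA3 estimates one quantity, the change over six months of ovarian suppression, and nothing in the plan relates it to the pre/post difference. A real fall is compatible with hormones explaining most of that difference or a small part of it.

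The second gap is specificity. The sentence names E2, but the intervention removes ovarian hormone secretion as a whole, from a luteal-phase baseline. Without an add-back group, a change cannot be assigned to E2 in particular. Without a control group, season, repeat testing and regression to the mean also remain possible explanations.

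What is at stake is interpretation. Section III itself reports that cold-induced BAT activity declines with age, so age is a recognised rival explanation for SA1 and SA2. The IV.E sentence licenses a conclusion about that rival which SA3 is not built to give.

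**Working it through.** **Inputs.** From Section IV.F: 32 evaluable women per group; two-sided 0.05; BAT oxidative metabolism SD 0.45 and difference 0.32 (thermoneutral), SD 0.66 and difference 0.50 (cold). From Section IV.D: n = 15 in SA3. Not in the documents: the within-woman correlation r between the two measurements. I assume 0.3 to 0.9.

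**The plan's own figures.** Two-sample t-test, noncentral t, 62 df:
- Thermoneutral: 0.32 / (0.45 × √(2/32)) = 2.84; power 79.96%. The plan states 80.0%.
- Cold: 0.50 / (0.66 × √(2/32)) = 3.03; power 84.7%, as stated.

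Both reproduce, so the SDs and differences can be carried over. The plan states no power or precision for SA3.

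**Precision of SA3.** SD of change = SD × √(2(1 − r)). Half-width = t(0.975, 14 df) × SD of change / √15, with t = 2.145.

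| r | Thermoneutral SD of change | Half-width | % of 0.32 | Cold SD of change | Half-width | % of 0.50 |
|---|---|---|---|---|---|---|
| 0.3 | 0.532 | 0.30 | 92% | 0.781 | 0.43 | 86% |
| 0.5 | 0.450 | 0.25 | 78% | 0.660 | 0.37 | 73% |
| 0.8 | 0.285 | 0.16 | 49% | 0.417 | 0.23 | 46% |
| 0.9 | 0.201 | 0.11 | 35% | 0.295 | 0.16 | 33% |

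**What a clear fall would say about share.** Take r = 0.9, the most favourable case. An observed thermoneutral fall of 0.12 has a CI of 0.12 ± 0.11, or 0.01 to 0.23, which excludes zero. Against 0.32, treated as known, that is 0.01/0.32 = 3% to 0.23/0.32 = 72%. At r = 0.5, a fall of 0.26 ± 0.25 gives 0.01 to 0.51, or 3% to 159%. Either result could be called a confirmed reduction. Neither places hormones above or below age.

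**Could the share be tested?** Suppose hormones explain the whole difference, and ask whether the SA3 change exceeds half the pre/post difference, treating the two estimates as independent. At thermoneutrality with r = 0.5, the SEs are 0.45/√15 = 0.116 for the change and 0.45 × √(2/32) = 0.1125 for the difference. The statistic is 0.16 / √(0.116² + 0.25 × 0.1125²) = 0.16/0.129 = 1.24, so the chance of passing 1.96 is about 24%. Over r = 0.5 to 0.8 it is 24% to 41% at thermoneutrality and 26% to 45% under cold.

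**Specificity, from the text.** Section IV.D says the agonist leads to prolonged suppression of pituitary gonadotropins and ovarian hormones. Section IV.E accepts that gonadotropins are low on the agonist but high after menopause. Section IV.D (Potential risks) expects fat mass to rise by about 1.0 to 1.5 kg, and Section III reports an inverse association between body fatness and cold-induced BAT activity. The one body-composition correction named in IV.E is REE per kg of fat-free mass, which does not touch the BAT endpoints.

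**The case against.** The strongest reply is that this is a cautious sentence in a discussion of limitations. It is conditional, it speaks of support and not proof, and it directly follows a candid admission about age. Section IV.F labels SA3 exploratory and plans no test or attribution step. All of that is true. A reader might infer that the plan will treat any fall, however small, as settling the matter; the text does not say so. What stands is that no criterion for *confirms* is given, and that what a confirmed fall is said to support is a ranking over age.

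A reader might also infer that this sentence is the plan's only answer to age confounding. It is not. Section IV.F adds to the regression any response-related variable that is unbalanced between the menopausal groups, and age would very likely qualify. However well that works, it concerns SA1 and SA2 and gives SA3 no means of ranking E2 against age.

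It is tempting to put a number on how often SA3 would mislead. If hormones explained 20% of the thermoneutral difference (0.064), the mean change would still be negative 71% of the time at r = 0.5. But that counts a negative mean alone as confirmation, which the documents do not say. If the 95% CI must exclude zero, the figure is about 7% to 21% for r = 0.3 to 0.9. The point does not depend on either figure.

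On specificity, Section IV.D measures estrone, E2, progesterone and testosterone and plans to correlate their changes with changes in the primary outcomes. Section III cites the team's randomised trial in which E2 add-back prevented the fall in REE. Section IV.E acknowledges the abrupt withdrawal and the different gonadotropin response. These are relevant background, but the add-back result is for REE and not BAT, and correlations in 15 women whose ovarian hormones are suppressed together do not isolate E2.

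Finally, SA3 is informative. Ageing over six months is negligible, so a fall would suggest that ovarian suppression contributes.

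**Conclusion.** The concern holds as a matter of inference. SA3 can at most suggest that ovarian hormone suppression contributes to lower BAT activity. It cannot rank E2 deficiency above age, because its change is not set against the pre/post difference, and it cannot isolate E2, because the agonist suppresses ovarian hormones together. A narrower interval alone would cure neither problem.

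Limited precision adds to this: the half-width is roughly a third to nine-tenths of the design difference in both conditions. That range rests on the assumed r of 0.3 to 0.9, on all 15 women being evaluable, and on SDs the protocol derives from a study of 12 men.

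A reader might go further and conclude that SA1 and SA2 are undermined. The documents do not support that: their estimates and tests are unaffected. What changes is the conclusion the trial may draw from SA3 about why the groups differ.

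**What to change.** Replace the inference sentence in Section IV.E with wording such as:

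*If the 95% CI for the SA3 change excludes zero in the direction of a reduction, this would be compatible with a contribution of ovarian hormone loss to the pre/post difference; it will not be used to conclude that E2 deficiency rather than age is the primary factor.*

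This supplies the missing criterion, names what the drug actually does, and matches the reporting already planned in Section IV.F.

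Optionally, show the SA3 change with its CI beside the SA1/SA2 difference, for description only. I would not add a ratio with a cut-off. Requiring the hormone share to exceed one half would succeed in well under half of trials even if hormones explained everything, and a ratio would still treat the whole uncontrolled change as hormonal and set six months of suppression against years of deficiency.

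The cost is one reworded sentence and, if wanted, one descriptive display. No participants, scans or arms are added. The downside is a weaker claim about E2.
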